2. Training and education in the ABC-ACC concept will reduce average glucose variability and HbA1c more than standard nutrition education (control). An accurate calculation of each patient's prandial insulin needs and assistance of a bolus calculator for calculating prandial insulin dose to reach a specific postprandial glucose target is more precise.
3. There are no differences in glycaemic effects between patients receiving training and education in the BCC concept versus the ABC-ACC concept. However, subgroups of patients with T1D may benefit more from the BCC concept compared to the ABC-ACC and vice versa (cf. sub-hypotheses).

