7.1 Sub-hypotheses

- BCC can be used to improve glycaemic control in patients with infrequent and limited (1-2 times/day) monitoring of plasma glucose values, if adherence to a guiding personalized carbohydrate plan is high
- Participants with low mathematical literacy will have greater improvements in glycaemic control practicing the BCC concept compared to the ABC-ACC concept due to a simpler educational meal plan approach focusing on training skills in estimating carbohydrate amounts and use of a guiding personalized carbohydrate meal plan
- Practising the ABC-ACC concept will improve the glycaemic control more than practising the BCC concept due to a more accurate dosing of meal insulin taking into account C:I ratios, insulin sensitivity factor active meal insulin
- Practicing ABC-ACC may induce weight gain, deleterious changes in body composition or lipidemic control due to higher flexibility in eating in terms of food choices thereby increasing the energy intake
- Diet-related quality of life may be higher using the ABC-ACC concept compared to the BCC concept due to a higher flexibility when practicing ABC-ACC, while participants' diet-related quality of life may drop in the BCC group due to a more rigorous dietary regimen aiming at eating a relatively fixed amount of carbohydrates at meals inducing a feeling of less freedom to eat as one wish
- Greater perceived competencies and support for autonomy will lead to improved glycaemic control through improved diabetes self-management
- Objective measurements of dietary adherence may improve the possibility of proving clinical effects of either the BCC or ABC-ACC concept in participants with high dietary adherence

8 Objectives

The overall objective is to compare the effect of two different nutritional programs (BCC and ABC-ACC) with the routine outpatient nutritional education on glycaemic control (HbA1c and plasma glucose variability) in adult patients with T1D after 6 months of intervention.

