13.2 Statistical methods

Intention-to-treat (ITT) analysis will be performed as the primary analysis on all primary and secondary outcomes after the last participant has participated in the last visit. Missing values will be handled with a last observation carried forward approach for ITT analysis. Per-protocol (PP) analysis will only be performed in case of sensitivity testing.

Parametric tests (general linear models) will be used to test differences in outcomes from baseline to follow-up. Heterogeneity in responsiveness to the interventions will be tested by dividing each intervention group into smaller groups based on data distribution (medians) or clinically meaningful cut-points. If model assumptions cannot be met even after logarithmic transformation, non-parametric tests will be used. Plots of residuals versus predicted values will be used to judge normality. Metabolic patterns will be tested with multivariate statistics. Adjustment for relevant confounders will be performed. Two-sided tests will be used. *P* values of <0.05 are considered significant. The statistical programs SPSS and SAS will be used for data analysis.

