13.3 Determination of sample size

Allowing for drop-outs (~20%) and subgroup analyses we plan to include a total of 231 patients in our study. This is based on sample size calculations which suggested that including 64 participants in each of the study groups would give us 80% power to detect a clinically meaningful difference in change in HbA1c of 3.5 mmol/mol between the BCC group versus the control group or the ABC-ACC group versus the control group with a 5% significance level using a two-sided test and an estimated standard deviation (SD) of 7 mmol/mol. This SD has previously been used for sample size calculations in ACC trials (28) and was similar to what we found in our evaluation of our BCC courses on mean changes and SD of HbA1c after 6 months in completers with T1D (n=185). MAGE has only been used as an outcome measure of glucose variability in a few randomized controlled dietary intervention studies of patients with diabetes (42, 43) showing differences in changes in MAGE up to 4.8 mmol/l (SD: 1.0) after a 12-week carbohydrate counting intervention (42). By including 77 participants in each study group we will have a power of 80% (alpha level of 0.05) in a two-sided test to detect a clinically meaningful difference in the change in MAGE during the intervention period (week 24) of ≥ 0.35 mmol/l (SD 0.7 mmol/l) between the study groups as presented in **Table 5**.

Table 5: Sample size calculations

Difference in HbA1c, mmol/mol (SD 7.0)	Difference in MAGE, mmol/l (SD 0.7)	Net total no of participants in the study (BCC group vs control or ABC-ACC group vs control)	No of participants given a dropout rate of 20%
2.0	0.20	582	698
3.0	0.30	261	315
3.5	0.35	192	230
4.0	0.40	150	180

14 Data management

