### Hypotheses for the primary outcomes:

1. We hypothesize that ACC is superior compared with usual dietary care (the control group) in reducing HbA1c or MAGE from baseline to end-of-treatment at week 24 (from V1 to V2).

Superiority is claimed if:

- a. the 95% confidence interval for the estimated difference in change between the groups for HbA1c or MAGE, estimated using a baseline corrected linear mixed model, excludes 0 and the P-value is <0.05: and,
- b. the estimated difference in HbA1c or MAGE between the two groups is equal to/surpass the minimal important difference in favour of the ACC group.

2. We hypothesize that BCC is superior compared with usual dietary care (control group) in reducing HbA1c or MAGE from baseline to end-of-treatment at week 24 (from V1 to V2).

Superiority is claimed if:

- c. the 95% confidence interval for the estimated difference in change between the groups for HbA1c or MAGE, estimated using a baseline corrected linear mixed model, excludes 0 and the P-value is <0.05: and,
- d. the estimated difference in HbA1c or MAGE between the two groups is equal to/surpass the minimal important difference in favour of the BCC group.

3. We hypothesize that BCC is equivalent to ACC in reducing HbA1c or MAGE from baseline to end-of-treatment at week 24 (from V1 to V2).

Equivalence is claimed if:

- e. The 90% confidence interval for the estimated difference in change between the groups for HbA1c or MAGE does not surpass minimal important difference in a negative or positive direction (16).

Hypotheses for the secondary outcomes can be found in the study protocol and [clinicaltrials.gov](https://clinicaltrials.gov).

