### **Other outcomes**

- Number of visits with dietitians, endocrinologists, and diabetes nurses at V2 and V3 in each group.
- Use of bolus calculator to assist insulin dose decision-making in the ACC arm collected after V2.
- Self-reported use of tools to estimate carbohydrate amounts in meals for each group at V1, V2, V3.
- Self-reported frequency and method for estimating mealtime insulin dose for each group at V1, V2, V3.
- Supplementary table with baseline characteristics for completers vs. non-completers with dropout before V2
  - Number of participants, n
  - Age (years)
  - Gender, male, n and %
  - Current smokers, n and %
  - Self-reported educational level
    - o Elementary school, n and %
    - o Upper secondary education, n and %
    - o Vocational, n and %
    - o Short further (< 3 y), n and %
    - o Medium further (3-4 y), n and %
    - o Long further (> 4 y), n and %
    - o Other education, n and %
  - Living alone, n and %
  - Body weight (kg)
  - BMI (kg/m^2)
  - Diabetes duration (years)
  - HbA1c (mmol/l)
- Supplementary table with extra baseline characteristics
  - Occupation
    - o Employed/self-employed, n and %
    - o Unemployed / job seeking, n and %
    - o Retired, n and %
    - o Other (on leave / studying), n and %
  - Annual household income (before tax)
    - o < 100,000 DKK (<13,500 EUR)
    - o 100,000 – 200,000 DKK (13,500 – 27,000 EUR)
    - o 200,000 – 400,000 DKK (27,000 – 54,000 EUR)
    - o 400,000 – 600,000 DKK (54,000 – 81,000 EUR)
    - o 600,000 – 800,000 DKK (81,000 – 108,000 EUR)
    - o 800,000 DKK (>108,000 EUR)
    - o Unspecified
  - Waist circumference, cm (women)
  - Waist circumference, cm (men)

- Fasting concentration of plasma lipids
  - o Total cholesterol (mmol/l)
  - o HDL cholesterol (mmol/l)
  - o Triglycerides (mmol/l)
- Dietary intake
  - o Total energy, kJ/day (women)
  - o Total energy, kJ/day (men)
  - o Carbohydrates, g/day (men)
  - o Carbohydrates, g/day (women)
  - o Carbohydrates, E%
- Physical activity level
  - o Low, n and %
  - o Moderate, n and %
  - o High, n and %
- Supplementary table with baseline-adjusted estimates for other secondary/exploratory outcomes
  - Glycaemic variability, standard deviation (SD), mmol/l
  - Average waist, cm
  - Fasting concentration of plasma lipids
    - o Total cholesterol (mmol/l)
    - o HDL cholesterol (mmol/l)
    - o Triglycerides (mmol/l)
  - Numeracy skills test, correct answers, %
  - Dietary intake (not measured at V3)

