## Analysis methods

Analyses of the primary outcomes will be performed based on efficacy estimates.

Before further analysis and before unblinding, all variables will be inspected to detect outliers to uncover potential errors, such as registration errors.

All continuous outcomes covered by this SAP will as a rule be modelled using baseline corrected repeated measures regression (22) with the following fixed effects and interactions between fixed effects: Visit, Visit (factorial)\*Treatment. Data from V1, V2, and V3 will be included in the analysis. The models will be specified with a restricted maximum likelihood estimation method and a repeat on participant level (unstructured covariance structure). Model fit will be evaluated using graphical methods before estimating the treatment effects and if necessary, outcomes will be log-transformed. Estimated mean differences (CI95%) between groups (CI95%), conditional means (CI95%), and within group changes (CI95%) will be extracted from the model. For log-transformed outcomes the results will be back-transformed and be presented as the ratio between estimated mean differences (CI95%), estimated conditional geometric means (CI95%) and relative changes within groups (CI95%), respectively. If log-transformation cannot meet distribution assumptions, a generalized mixed linear model with an appropriate distribution will be applied instead of the repeated measures regression model. In case the distribution does not comply with the distributions available in the generalized mixed linear model a non-parametric test will be used to compare the change scores for the given outcome.

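### The sub-hypothesis that low-numeracy participants do better on BCC than on ABC-ACC has no valid prespecified test in either document

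*Protocol*

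**What the plan says.** Main hypothesis 3 (Protocol section 7) expects no overall glycaemic difference between BCC and ABC-ACC, but adds that "subgroups of patients with T1D may benefit more from the BCC concept compared to the ABC-ACC and vice versa" and points to the sub-hypotheses. The relevant one in Protocol 7.1 reads: "Participants with low mathematical literacy will have greater improvements in glycaemic control practicing the BCC concept compared to the ABC-ACC concept".

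Protocol 13.2 gives a single method for differences in response: "Heterogeneity in responsiveness to the interventions will be tested by dividing each intervention group into smaller groups based on data distribution (medians"; the sentence goes on to allow clinical cut-points instead of medians. Numeracy is not mentioned there, nor is any treatment-by-moderator term. Protocol 13.3 opens with "Allowing for drop-outs (~20%) and subgroup analyses we plan to include a total of 231 patients in our study".

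The SAP model (Analysis methods) has "fixed effects and interactions between fixed effects: Visit, Visit (factorial)\*Treatment" and no moderator. Its Additional analyses section declares the topic not relevant and gives no reason. Numeracy survives only as an outcome in a supplementary table ("Numeracy skills test, correct answers", in per cent). For the remaining hypotheses the SAP refers the reader elsewhere: "Hypotheses for the secondary outcomes can be found in the study protocol and" the registry. For sample size it refers to the protocol.

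The mathematical literacy test is completed at V1 (Protocol 10.7, 11.3 and Table 1), so a pre-intervention score exists for use as a moderator.

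**The concern.** The sub-hypothesis says that the BCC versus ABC-ACC difference depends on numeracy. Testing it needs a comparison of that difference across numeracy levels. Dividing each group and comparing its high and low scorers does not supply this. Within one arm, high and low scorers may differ because numeracy is prognostic, with no bearing on which programme suits them. A significant split in one arm and a non-significant one in the other could then be read as evidence that numeracy matters for one programme only. Any dichotomy also discards information from a graded score.

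The two documents also disagree on whether heterogeneity is examined at all: the protocol says it will be tested and that the sample size allows for it, and the SAP leaves it out. If the matter stays unresolved when analysis starts, any numeracy result will be post hoc, and the choice of split will be open.

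**Working it through.** **Inputs from Protocol 13.3.** HbA1c difference 3.5 mmol/mol, SD 7, two-sided 5%, 80% power, 20% dropout, 231 in total.

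**Assumptions not in the documents.** Numeracy is roughly normal and scaled per SD. Its slope is non-zero in one of the two arms. Residual SD is 7. For dichotomies, the halves are equal. Evaluable number: 77 × 0.8 = 61.6, taken as 62 per arm.

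**1. The plan's own figure.** A two-sample t-test at 3.5/7 = 0.5 SD gives 63.77, so 64 per group and 192 net, which matches Table 5. Then 64 × 1.2 = 76.8, so 77, and 3 × 77 = 231. The whole total is the primary comparison plus the dropout margin. No participants are added for subgroups.

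**2. What a within-arm split shows when there is no interaction.** Let numeracy be equally prognostic in both arms, with slope b. Two halves of a normal score differ on average by 2√(2/π) = 1.596 SD. The standard error of a high-low comparison in one arm is 7 × √(2/31) = 1.78.

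| b (mmol/mol per SD) | High-low difference | Chance p that one arm is significant | Exactly one arm significant, 2p(1−p) |
|---|---|---|---|
| 1 | 1.60 | 0.15 | 25% |
| 2 | 3.19 | 0.43 | 49% |

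Simulation gives 24% and 49%. With no effect modification, the within-arm reading would suggest it a quarter to a half of the time.

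**3. Power of a proper interaction test, BCC versus ABC-ACC.**

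Continuous score: SE of the slope difference = 7 × √(2/62) = 1.257. At a slope difference of 2.2, 2.2/1.257 = 1.75, and Φ(1.75 − 1.96) is about 42% by the normal approximation. Simulation with the t-test gives about 39%.

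Median split: SE of the difference of differences = 7 × √(4/31) = 2.51. A slope of 2.2 per SD corresponds to 2.2 × 1.596 = 3.5 mmol/mol between halves. Then 3.5/2.51 = 1.39, and Φ(1.39 − 1.96) is about 28%. Simulation gives 27%.

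Simulated power at three assumed slopes:

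| Slope difference per SD | High-low contrast | Continuous | Median split |
|---|---|---|---|
| 2.2 | 3.5 | 39% | 27% |
| 2.5 | 4.0 | 49% | 34% |
| 3.5 | 5.6 | 76% | 57% |

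**4. The subgroup allowance.** With 64 evaluable per arm in equal halves, a split interaction test has 29% power for 3.5 mmol/mol. It reaches 80% only at 6.9 mmol/mol, about twice the trial's minimal important difference. About 252 evaluable per arm would be needed to detect 3.5.

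**The case against.** The strongest reply is that Protocol 13.2 is vague rather than wrong. It mentions heterogeneity directly after general linear models, so a between-arm interaction may have been intended. It also allows clinical cut-points, which would be common to all arms, and it does not say that medians are arm-specific. This stands in part: a within-arm comparison with arm-specific cuts is one reading, not the stated plan. But the sentence names no moderator, cut-point or interaction on any reading, and every version of it dichotomises.

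A second reply is that if the SAP governs, no split will be done and criticism of it is moot. That is fair as far as it goes. What remains is a protocol hypothesis with no analysis, and a sample-size statement that the SAP still cites.

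A third reply is that power is low whichever method is used and no primary conclusion changes. That is correct, and it limits the weight of the point.

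A reader might infer more than the documents support:

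- **That the hypothesis cannot be tested.** The V1 score and the arm are both recorded, so an interaction can be fitted. What is missing is prespecification.
- **That matching patients to programmes is the trial's main purpose.** The objectives compare each programme with routine education. Numeracy is one of seven sub-hypotheses.
- **That between-arm tests in the two halves would disagree about half the time with no interaction.** That needs a true 3.5 mmol/mol BCC versus ABC-ACC difference in both halves, and hypothesis 3 expects none. With no difference, discordance is 2 × 0.05 × 0.95 = 9.5%. The 25% to 49% in the working concerns within-arm splits with prognostic numeracy.

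**Conclusion.** The point holds in limited form: the numeracy sub-hypothesis has no valid prespecified test. The protocol's method states no between-arm interaction. The SAP drops the topic without explanation. The claimed allowance for subgroups is not in the 231.

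At the assumed slopes, a continuous score gains 12 to 19 percentage points of power over a median split (39% against 27%, up to 76% against 57%). These figures rest on 62 evaluable per arm, SD 7 and a normally distributed score. The interaction sizes are illustrative because the documents give none. At a high-low contrast of 3.5 mmol/mol, even the better method misses a true interaction more often than it finds one, so the result can only be exploratory. This is a secondary matter, worth correcting because the correction is cheap and is prespecified only if made before analysis.

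**What to change.** In the SAP, before analysis begins, replace the entry under Additional analyses with one analysis labelled exploratory:

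- Add the continuous V1 numeracy score (per cent correct), and its interactions with visit and with visit-by-treatment, to the HbA1c and MAGE models.
- Report the BCC versus ABC-ACC interaction at the SAP's V2 (week 24) with its 95% CI, and the predicted BCC versus ABC-ACC difference at stated low and high scores.
- State that this replaces the division into smaller groups in Protocol 13.2, and that significance within separate halves will not be interpreted.

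Remove the reference to subgroup analyses from Protocol 13.3. If the team does not want the analysis, the minimum is to state in the SAP that the sub-hypothesis will not be tested, and still correct 13.3. If analysis has already started, label the result post hoc.

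The cost is a few lines of text and code, with no new data. The drawback is limited power: the interval will be wide, and a null result will not show that numeracy is irrelevant.

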13.3 Determination of sample size

Allowing for drop-outs (~20%) and subgroup analyses we plan to include a total of 231 patients in our study. This is based on sample size calculations which suggested that including 64 participants in each of the study groups would give us 80% power to detect a clinically meaningful difference in change in HbA1c of 3.5 mmol/mol between the BCC group versus the control group or the ABC-ACC group versus the control group with a 5% significance level using a two-sided test and an estimated standard deviation (SD) of 7 mmol/mol. This SD has previously been used for sample size calculations in ACC trials (28) and was similar to what we found in our evaluation of our BCC courses on mean changes and SD of HbA1c after 6 months in completers with T1D (n=185). MAGE has only been used as an outcome measure of glucose variability in a few randomized controlled dietary intervention studies of patients with diabetes (42, 43) showing differences in changes in MAGE up to 4.8 mmol/l (SD: 1.0) after a 12-week carbohydrate counting intervention (42). By including 77 participants in each study group we will have a power of 80% (alpha level of 0.05) in a two-sided test to detect a clinically meaningful difference in the change in MAGE during the intervention period (week 24) of ≥ 0.35 mmol/l (SD 0.7 mmol/l) between the study groups as presented in **Table 5**.

Table 5: Sample size calculations

Difference in HbA1c, mmol/mol (SD 7.0)	Difference in MAGE, mmol/l (SD 0.7)	Net total no of participants in the study (BCC group vs control or ABC-ACC group vs control)	No of participants given a dropout rate of 20%
2.0	0.20	582	698
3.0	0.30	261	315
3.5	0.35	192	230
4.0	0.40	150	180

14 Data management

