9.5.3 Criteria for withdrawal

One or more of these criteria will result in withdrawal of the participant from the study:

- Participant withdraws the informed consent
- Pregnancy or other safety concerns, as judged by the investigator
- Participant's general condition contraindicates continuing the study, as judged by the investigator or a medical expert
- Non-compliance with the study protocol or lack of corporation as judged by the investigator
- Lost to follow-up
- Other reasons determined by the investigator

Participation in the study is voluntary, and participants have the right to withdraw from the study without providing a reason and with no loss of benefits to which the participant is entitled. If a participant chose to withdraw the study personnel and investigator must be informed immediately, and every effort should be made to complete the early termination assessments and document the reason for discontinuation. For participants considered lost to follow-up, the last completed visit will be recorded. The investigator has the right to terminate participation of any participant at any time if they deem it in the participant's best interest. Study participants will not be excluded from the study if they do not attend all visits.

Participants who withdraw from the study will not be replaced. Follow-up will be performed for withdrawn participants at the end of the study and used in analyses if allowed by the participant.

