9.8 Randomization

Participants eligible for inclusion in the study according to the screening will have the baseline measurements collected followed by a randomization carried out by the study investigator/study personnel.

A total of 231 participants will be randomly allocated in a 1:1:1 ratio to one of the following three groups:

- 1) BCC
- 2) ABC-ACC
- 3) Control

Randomization will be performed by the investigator at visit 1 (V1) after the baseline examination. Participants will be randomly assigned to one of three groups with a 1:1:1 allocation by use of a computer-

generated randomization schedule in REDCap. The randomization list will be generated and kept securely by the clinical responsible investigator. The randomization is done by stratifying the participants based on sex and HbA1c at baseline. The randomization is done in blocks in to order to ensure an equal number of participants in each group.

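### The 20% drop-out allowance in Protocol Table 5 multiplies by 1.2 instead of dividing by 0.8, so 231 covers only about 17% loss and leaves nothing for subgroups

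*Protocol*

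**What the plan says.** Protocol 13.3 opens with the planned total: "Allowing for drop-outs (~20%) and subgroup analyses we plan to include a total of 231 patients in our study". For HbA1c it states that "including 64 participants in each of the study groups would give us 80% power" to detect 3.5 mmol/mol with SD 7 mmol/mol, two-sided at 5%. For MAGE it states: "By including 77 participants in each study group we will have a power of 80% (alpha level of 0.05"), two-sided, for 0.35 mmol/l with SD 0.7 mmol/l.

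Table 5 puts both outcomes on the same rows. One column gives net totals of 582, 261, 192 and 150. The next, headed "No of participants given a dropout rate of 20" per cent, gives 698, 315, 230 and 180.

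Protocol 9.8 confirms the number randomised: "A total of 231 participants will be randomly allocated in a 1:1:1 ratio". Protocol 9.5.3 adds "Participants who withdraw from the study will not be replaced" but also "Follow-up will be performed for withdrawn participants at the end of the study and used in analyses if allowed by the participant". On subgroups, Protocol 13.2 says: "Heterogeneity in responsiveness to the interventions will be tested by dividing each intervention group into smaller groups", at medians or clinical cut-points.

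The Sample size entry in SAP Section 3 only points to the protocol. The Additional analyses entry in SAP Section 6 lists none.

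**The concern.** If a fraction of those enrolled is lost, the number enrolled must be the evaluable number divided by the fraction retained. Multiplying by one plus the loss gives too few, and the Table 5 totals look like the result of that multiplication. The opening sentence of 13.3 also says the total covers a second need, subgroup analyses, yet 231 appears to be fully explained by the drop-out step.

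What is at stake is the accuracy of the stated design. As written, a reader would take 231 to protect 80% power at 20% drop-out and still leave room for subgroups. Because the SAP adopts the protocol text by reference, both statements would pass into the trial reports unless corrected. Protocol 13.3 also uses the same verb for 64 and for 77 participants per group and attaches 80% power to each, so the reader has to work out which number is evaluable and which is enrolled.

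**Working it through.** **Inputs (Protocol 13.3 and Table 5).** Two-sided alpha 0.05, power 80%, SD 7 mmol/mol for HbA1c and 0.7 mmol/l for MAGE, three equal groups, drop-out 20%. In every row the two outcomes have the same standardised difference; in the design row 3.5/7 = 0.35/0.7 = 0.5.

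**Step 1: reproduce the net column.** For a two-sample t-test with n per group and standardised difference d, power is the probability that |T| exceeds its 5% critical value, where T has 2n - 2 degrees of freedom and non-centrality d x sqrt(n/2). The smallest n giving 80% is 194, 87, 64 and 50 per group. Times 3 this is 582, 261, 192 and 150, which matches Table 5 exactly.

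**Step 2: reproduce the drop-out column, then correct it.**

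| Difference (mmol/mol) | Net total | Net x 1.2 | Stated | Net per group / 0.8, rounded up, x 3 | Loss the stated total can absorb |
|---|---|---|---|---|---|
| 2.0 | 582 | 698.4 | 698 | 243 x 3 = 729 | 1 - 582/698 = 16.6% |
| 3.0 | 261 | 313.2 | 315 | 109 x 3 = 327 | 1 - 261/315 = 17.1% |
| 3.5 | 192 | 230.4 | 230 | 80 x 3 = 240 | 1 - 192/230 = 16.5% |
| 4.0 | 150 | 180.0 | 180 | 63 x 3 = 189 | 1 - 150/180 = 16.7% |

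The stated column follows the factor 1.2 in every row. The 315 is 87 x 1.2 = 104.4, rounded up to 105 per group, times 3. Rounding the corrected figures on the total instead gives 728, 327, 240 and 188. No stated row reaches its corrected value under either rounding.

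**Step 3: trace 231.** 64 x 1.2 = 76.8, rounded up to 77; 77 x 3 = 231. The drop-out step alone produces the whole total, so no participant is added for subgroups. The total keeps 64 evaluable per group up to 1 - 64/77 = 16.9% loss. Full cover at 20% would need 64/0.8 = 80 per group, which is 240 in all, or 9 more.

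**Step 4: power at a true 20% loss.** 77 x 0.8 = 61.6 per group. With d = 0.5:

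- 61.6 analysed per group: non-centrality 0.5 x sqrt(30.8) = 2.775, power 78.6%
- 64 analysed per group: non-centrality 0.5 x sqrt(32) = 2.828, power 80.1%
- 77 analysed per group: non-centrality 0.5 x sqrt(38.5) = 3.102, power 86.9%

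The slip costs about 1.5 percentage points. The last line also shows that 77 cannot be an analysed number with 80% power. It has to be the number enrolled, with 64 the evaluable number.

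**Step 5: what baseline correction might recover.** Assume that 7 is the SD of the change, that baseline and week-24 variances are equal, and that the correlation between them is r. Adjusting for baseline then multiplies the SD of change by sqrt((1 + r)/2). The documents do not give r. At 61.6 per group, power is 88.9% for r = 0.5, 84.8% for r = 0.7 and 80.6% for r = 0.9. It falls below 80% only above about r = 0.93.

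**The case against.** The strongest reply is that the calculation in 13.3 is not the planned analysis. Protocol 13.2 plans intention-to-treat with last observation carried forward and adjustment for confounders, and the SAP replaces this with a baseline-corrected mixed model. Carrying values forward keeps drop-outs in the analysed number, though possibly with a diluted effect. Protocol 9.5.3 provides for follow-up of withdrawn participants, so data loss may be smaller than drop-out. The text also says about 20%, and the plan tolerates nearly 17%. All of this stands, and it rules out the stronger inference that the trial is materially underpowered. It does not rescue the column: Table 5 states 20% without qualification, and every row is the net number times 1.2.

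A second reading is that 64 and 77 are contradictory power claims. The documents do not support that. Table 5 separates net from inflated totals, the MAGE sentence refers to that table, and Protocol 9.2 and 9.8 give 77 and 231 as the numbers randomised. What remains is loose wording. One might instead suppose that 77 reflects a halved alpha: two-sided 0.025 gives 77 by normal approximation (79.8% power by t-test). But 13.3 states 0.05 and mentions no split, so the match appears coincidental.

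A third is that the missing subgroup allowance weakens an analysis in the SAP. It does not, since the SAP plans no subgroup analysis. The point concerns only the protocol's sentence, and the protocol sets no target difference for subgroups against which a shortfall could be measured.

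Finally, the SAP describes randomisation in the past tense and will report losses and missing data by group, so no decision now turns on the planning rate. That supports a light remedy, not leaving the figures as they are.

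**Conclusion.** The point holds as a minor arithmetic and reporting error. Two statements in 13.3 are wrong as written: the Table 5 drop-out column does not correspond to 20% loss, and 231 contains no allowance for subgroup analyses. A third, the 80% attached to both 64 and 77, needs only a clarification of evaluable against enrolled. The size is 9 participants at the design difference, or about 1.5 points of power for the significance test if exactly 20% are lost.

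The corrected totals rest only on the protocol's own inputs and on drop-outs contributing no week-24 data. The power loss also assumes the unadjusted t-test used for the sample size. Under the SAP's model the loss is probably recovered, but that depends on a correlation the documents do not state.

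**What to change.** Replace the cross-reference in the SAP's Sample size section with a short statement along these lines:

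> Sixty-four evaluable participants per group give 80% power (unadjusted two-sample t-test, two-sided 5%) for a difference of 3.5 mmol/mol in HbA1c with SD 7, or 0.35 mmol/l in MAGE with SD 0.7. The plan was to enrol 77 per group (231), which keeps 64 evaluable up to about 17% drop-out. At 20% drop-out about 62 per group remain, with about 79% unadjusted power; the baseline-corrected model may recover this. No allowance is made for subgroup analyses.

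Add a note that the Table 5 drop-out column should read 729, 327, 240 and 189, rounded up per group. Leave the protocol text in place as the prospective record, and do not change enrolment or any analysis.

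The cost is one SAP paragraph and one note. If a protocol erratum is preferred and counts as an amendment, Protocol 15.5 requires the protocol's signatories to sign it.
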